6.4.1.2. Patients Discontinuing Concomitant Preventive Medications during the Treatment Period

If a patient used preventive migraine medication at baseline, stopped the medicine during the treatment period and did not resume the medication through the EOT visit, he/she will be counted as a patient discontinuing concomitant preventive medication during the treatment.

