First treatment administration (ie, for this study) will occur at visit 2, and additional doses will be administered at each visit (approximately every 4 weeks) through visit 13. Patients will return for the EOT visit (visit 14) approximately 4 weeks after administration of the final dose of study drug, and they will return approximately 7.5 months (225 days [the approximate equivalent of 5 half-lives]) after administration of the final dose of the study drug for collection of adverse event and concomitant medication information and samples for pharmacokinetic, immunogenicity, and biomarker analyses.

Headache information will be captured using an electronic headache diary device as follows:

- For patients rolling over from the pivotal efficacy studies, headache information will be captured daily during the first 3 months, during the 4-week period after visit 7, and during the 4-week period after visit 13.

- For patients not rolling over from the pivotal efficacy studies, headache information will be captured daily during the first 4 months, during the 4-week period after visit 7, and during the 4-week period after visit 13.

Assessments of migraine-related disability and change in quality of life (using the HIT-6 or MIDAS questionnaire, PHQ-2/PHQ-9, PGIC scale, MSQOL questionnaire, EQ-5D-5L questionnaire, and WPAI questionnaire), safety evaluations, and collection of pharmacokinetic, immunogenicity, and biomarker samples will be performed throughout the study according to the schedules of assessments ([Table 1](#), [Table 2](#), and [Table 3](#)) and [Section 3.14](#).

[figure not shown]
Patients who withdraw from the study before completing the 12-month treatment period will have EOT visit (visit 14) procedures and assessments performed at their final visit, and they will be asked to return for the follow-up visit approximately 7.5 months (225 days [the approximate equivalent of 5 half-lives]) after their last dose of study drug.

The study schemas for patients with CM and EM who receive study drug in the current study are presented in [Figure 1](#) and [Figure 2](#), respectively.

The end of the study is defined as the date the last patient attends the follow-up visit (visit 15).

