1.3. Exploratory Objectives

The exploratory objectives of the study are as follows:

- to evaluate the efficacy of sc TEV-48125 in patients with migraine, as assessed by the reduction of the number of migraine days
- to evaluate the efficacy of sc TEV-48125 in patients with migraine, as assessed by the reduction in the number of headache days of at least moderate severity
- to evaluate the efficacy of sc TEV-48125 in patients with migraine, as assessed by the reduction in the number of migraine days in patients not receiving concomitant migraine preventive medications at baseline
- to evaluate the efficacy of sc TEV-48125 in patients with migraine, as assessed by the reduction in the number of headache days of at least moderate severity in patients not receiving concomitant migraine preventive medications at baseline
- to evaluate the efficacy of sc TEV-48125 in patients with migraine, as assessed by the reduction in the number of migraine days for new patients and placebo-treated rollover patients
- to evaluate the efficacy of sc TEV-48125 in patients with migraine, as assessed by the reduction in the number of headache days of at least moderate severity for new patients and placebo-treated rollover patients
- to evaluate the efficacy of sc TEV-48125 in patients with migraine, as assessed by the reduction of the number of headache days of any severity
- to evaluate the efficacy of sc TEV-48125 in patients with migraine, as assessed by the reduction of the use of any acute headache medications
- to evaluate the efficacy of sc TEV-48125 in patients with migraine, as assessed by the discontinuation of use of concomitant preventive medications
- to evaluate the efficacy of sc TEV-48125 in patients with migraine, as assessed by the reduction of migraine-related disability and change in quality of life
- to evaluate the immunogenicity of TEV-48125 and the impact of antidrug antibodies (ADAs) on clinical outcome in patients exposed to sc TEV-48125
- to explore the correlation between pharmacokinetic parameters and drug efficacy

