^a Patients not rolling over from the pivotal efficacy study who meet eligibility criteria after completing a 28-day run-in period and patients rolling over from the pivotal efficacy study who received placebo will be randomized in a 1:1 ratio at visit 2 to receive a loading dose of TEV-48125 at 675 mg followed by monthly TEV-48125 at 225 mg or TEV-48125 at 675 mg quarterly.

^b For patients who begin this study (visit 2) on the same day as the EOT visit (visit 5) of the pivotal efficacy studies, the EOT visit procedures/assessments for the pivotal efficacy study must be completed before beginning visit 2 procedures/assessments.

EOT=end-of-treatment; NR=nonrollover patients; PBO=placebo; V=visit.

Figure 2: Study Schema for Patients with Episodic Migraine

^a Patients rolling over from the pivotal efficacy study who received placebo and patients not rolling over from the pivotal efficacy study who meet eligibility criteria after completing a 28-day run-in period will be randomized in a 1:1 ratio at visit 2 to receive quarterly TEV-48125 at 675 mg or monthly TEV-48125 at 225 mg.

^b For patients who begin this study (visit 2) on the same day as the EOT visit (visit 5) of the pivotal efficacy study, the EOT visit procedures/assessments for the pivotal efficacy study must be completed before beginning visit 2 procedures/assessments. EOT=end-of-treatment; NR=nonrollover patients; PBO=placebo; V=visit.

Table 1: Study Procedures and Assessments for Patients Rolling Over from the Pivotal Efficacy Studies

Study period	Pre-treatment period ^a	Treatment period													Follow-up period	
Visit number	V1	V2 ^b	V3	V4	V5	V6	V7	V8	V9	V10	V11	V12	V13	V14	V15	
Procedures and assessments (completed before dosing, when applicable, unless otherwise noted)	Screening days -28 to -1	Dose 1 day 0 (±5 days)	Dose 2 day 28 (±5 days)	Dose 3 day 56 (±5 days)	Dose 4 day 84 (±5 days)	Dose 5 day 112 (±5 days)	Dose 6 day 140 (±5 days)	Dose 7 day 168 (±5 days)	Dose 8 day 196 (±5 days)	Dose 9 day 224 (±5 days)	Dose 10 day 252 (±5 days)	Dose 11 day 280 (±5 days)	Dose 12 day 308 (±5 days)	EOT/early withdrawal day 336 (±5 days)	Final visit day 533 (±15 days)	
Informed consent		X														
Inclusion and exclusion criteria		X														
Randomization ^c		X														
Full physical examination, including weight		X ^d					X	X					X	X	X	
12-lead ECG ^e		X ^d												X		
Vital signs measurement ^e		X ^d	X	X	X	X	X	X	X	X	X	X	X	X		

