2.3. Sample Size and Power Considerations

There are no statistical considerations for this sample size. A total of 1842 patients (867 patients from Study TV48125-CNS-30049, 675 patients from Study TV48125-30050, and approximately 300 patients who did not participate in the pivotal efficacy studies) are planned for enrollment, and a 30% drop-out rate is anticipated.

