4.6. Study Days and Visit Windows

Study days will be numbered relative to the 1st day of study drug administration. The start of treatment (visit 2 or day 1) is defined as the date on which a patient receives the 1st dose of study drug, as recorded on the study drug diary. The 1st day for the patients rolling over from the pivotal efficacy studies will be the day when they receive the 1st dose of study drug after finishing their procedures/assessments for the pivotal study EOT visit ([Figure 1](#) and [Figure 2](#)). Days will be numbered relative to study start (ie, ..., -2, -1, 1, 2, ...; with day 1 being the start of study drug and day -1 being the day before the start of study drug).

The 4-week (28-day) visit windows for the e-diary based efficacy endpoints will be determined based on the actual dosing day. The run-in phase for the new patients is defined as day -28 to -1 before the 1st injection on day 1. Treatment is from the visit 2 to visit 14 or the EOT visit. Month 1 is from the date/time of the 1st dose of study drug administration on day 1 to the date/time just

before the 2nd dose. Month 2 is from the date/time of the 2nd dose to the date/time just before the 3rd dose. Month 3 is from the date/time of the 3rd dose, and so on.

Throughout this document, all by month efficacy summaries for the headache data will refer to these visit windows.

For all other by-visit summaries, if there are multiple assessments at a postbaseline visit then the last non-missing assessment at that visit will be used for the summary. This includes assessments at the scheduled and unscheduled visits.

Endpoint for analyses and summaries is the last observed postbaseline data. For patients who withdraw from the study, their safety data at the early termination visit will be excluded from the by-visit summaries but will be included in the endpoint summaries.

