6.4.1. Variable Definition

6.4.1.1. Headache Diary Data

The exploratory efficacy variables derived from the headache e-diary data include mean change from baseline in the monthly average number of migraine days, headache days of at least moderate severity, headache days of any severity, days of use of any acute headache medications, headache hours of at least moderate severity, headache hours of any severity, days with nausea or vomiting, days with photophobia and phonophobia *during the 4-week periods* after visits 2, 3, 4, 7, and 13 for months 1, 2, 3, 6, and 12. The change from baseline is calculated as *postbaseline value – baseline value*, where the postbaseline values are derived using formula (1) in Section 6.1 and the baseline values are carried forward from the pivotal studies or calculated using formula (2) in Section 6.1 for new patients

If a patient has missing days of entries in the e-diary for a month, his/her monthly average number of days of study variables *during the 4-week period* for that month will be handled as discussed in Section 4.5.

The percent reduction in the monthly average number of migraine days *during the 4-week period* after each dose at visits 2, 3, 4, 7, and 13 for months 1, 2, 3, 6, and 12 will be calculated by formula (3) in Section 6.1. The patient is considered as a responder reaching 50%, 75%, or 100% reduction if his/her percent reduction is 50% or more, 75% or more, or 100%, respectively. Similar definition will be applied to calculate the proportion of patients reaching at least 50%, 75%, or 100% reduction in the monthly average number of headache days of at least moderate severity during the 4-week period for months 1, 2, 3, 6 and 12. If a patient is early discontinued from the study, he/she will be counted as a non-responder.

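### The preventive-discontinuation endpoint (SAP 6.4.1.2) follows early leavers only to their withdrawal visit, so it can count them as discontinuing, while the diary responder endpoints score early leavers as non-responders

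*SAP*

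**What the plan says.** SAP 6.4.1.2 sets three conditions: preventive use at baseline, a stop during treatment, and no resumption up to the end-of-treatment visit. If the patient stopped and "did not resume the medication through the EOT visit, he/she will be counted as a patient discontinuing concomitant preventive medication". It sets no minimum time off the preventive and has no rule for patients who leave early.

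The result is read as efficacy. SAP 1.3 lists, among the ways efficacy is to be assessed, the "discontinuation of use of concomitant preventive medications". SAP 6.4.2.2 takes the proportion over patients who used concomitant preventives, and SAP 6.1 uses the FAS for all efficacy analyses. Early leavers are therefore in the denominator.

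For the 50%, 75% and 100% reduction endpoints, SAP 6.4.1.1 does have a rule for leavers: "If a patient is early discontinued from the study, he/she will be counted as a non-responder".

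SAP 2.3 gives the planned enrolment "and a 30% drop-out rate is anticipated".

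**The concern.** The no-resumption condition works only if patients are watched for a comparable time. If the end-of-treatment visit moves forward to the day a patient withdraws, a leaver has to stay off the preventive only until that day. A completer who stopped at the same time has to stay off it until about day 336. The same person may then be a non-responder on migraine days and a favourable count on preventive discontinuation.

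What is at stake is how one listed efficacy objective is read. No hypothesis test is planned, so the reported proportion is the whole result for that objective.

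**Working it through.** The plan states no expected value for this endpoint, so there is no figure to reproduce. The check has a textual part and an illustrative calculation.

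**1. Which visit ends observation for a leaver?**

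- Protocol 3.1: patients who withdraw before completing treatment "will have EOT visit (visit 14) procedures and assessments performed at their final visit".
- SAP 2.1, Tables 1 and 2: the visit 14 column is headed "EOT/early withdrawal day 336 (±5 days"), one column for both events.
- SAP 4.6: "Treatment is from the visit 2 to visit 14 or the EOT visit". The two can therefore differ.
- SAP 7.2: treatment duration uses the end-of-treatment day and the early-withdrawal day interchangeably.

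Together these place a leaver's end-of-treatment visit at withdrawal.

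**2. Apply the rule to one patient.** Suppose a baseline user stops the preventive at month 2 and leaves at month 3. The no-resumption condition covers about 1 month (3 − 2). For a completer who stops at month 2 it covers about 10 months (12 − 2). The leaver meets the definition. The schedule tables allow standard of care after the early-withdrawal visit, so a preventive restarted then falls outside the window.

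**3. Compare endpoints.** SAP 6.4.1.1 scores that patient as a non-responder. SAP 6.4.1.2 counts the patient as discontinuing.

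**4. Size, for illustration.** Let d be the drop-out proportion, p_c the stop rate among completers and p_l the proportion of leavers who have stopped, and not restarted, by the time they leave.

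- As written: (1 − d)·p_c + d·p_l
- Leavers not counted as meeting the endpoint: (1 − d)·p_c
- Difference: d·p_l, which does not depend on p_c or on the number of users

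d = 0.30 is from SAP 2.3. Applying it to preventive users is an assumption, and p_c and p_l are assumed throughout.

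| p_c | p_l | As written | Leavers not counted | Difference (points) |
|---|---|---|---|---|
| 10% | 5% | 0.070 + 0.015 = 8.5% | 7.0% | 1.5 |
| 10% | 10% | 0.070 + 0.030 = 10.0% | 7.0% | 3.0 |
| 10% | 20% | 0.070 + 0.060 = 13.0% | 7.0% | 6.0 |
| 20% | 5% | 0.140 + 0.015 = 15.5% | 14.0% | 1.5 |
| 20% | 10% | 0.140 + 0.030 = 17.0% | 14.0% | 3.0 |
| 20% | 20% | 0.140 + 0.060 = 20.0% | 14.0% | 6.0 |

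In patients: planned rollovers are 867 + 675 = 1542. At the 30% ceiling on preventive use in the pivotal studies (SAP 2.1), that is about 463 users, of whom 0.30 × 463 ≈ 139 would leave early. At p_l of 5%, 10% or 20%, about 7, 14 or 28 patients change category. New patients are left out because the documents give no preventive-use rate for them.

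**The case against.** **The reading of the visit is inferred.** SAP 6.4.1.2 does not mention leavers. Protocol 3.14.3.1.11 ties the end-of-treatment visit to day 336, and SAP 4.6 also speaks of a separate early termination visit. One could hold that a leaver simply has no defined status. That is possible, but it conflicts with the combined column heading and with the treatment-period and duration rules in SAP 4.6 and 7.2. Even on that reading the section needs a sentence on leavers.

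**The comparison with SAP 6.4.1.1 has limits.** Its non-responder rule is written for the diary responder endpoints, where leavers lack later diary months. Stopping a preventive is an observed, dated event, and the protocol's wording of the endpoint carries no durability condition. This stands, and it is why the point is inconsistency rather than breach. But SAP 6.4.1.2 itself added a no-resumption condition, which is now applied over unequal follow-up.

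**The direction is not one-sided.** Shorter follow-up leaves less time to resume and also less time to stop. This stands.

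**Restarts are still recorded.** Leavers are asked back about 7.5 months after the last dose, concomitant medication is collected then, and SAP 7.11 summarises it to the end of the study. True, but the endpoint definition does not use it.

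**A stronger reading is tempting.** A reader might infer that treatment failures are credited as successes and the proportion heavily inflated, for example 13.0% against 7.0%. The documents do not support that. They give no stop rates, and patients leave for reasons other than lack of efficacy, including adverse events and withdrawn consent (Protocol 3.12). That contrast also assumes leavers stop at twice the completers' rate, and the 7.0% is a convention, not the true value. If both groups stop at 10%, the rule as written returns 10.0%, which is the actual proportion who stopped.

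**Conclusion.** The concern holds as an inconsistency. As written, a baseline user who stops the preventive and then withdraws is counted as discontinuing after a shortened observation period, whereas the diary responder endpoints count early leavers against the treatment. At 30% drop-out the choice of convention moves the proportion by 0.30 times the leavers' stop rate, or 1.5 to 6.0 points for assumed rates of 5% to 20%. The share of that difference that is bias cannot be determined from the documents.

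The conclusion rests on reading the end-of-treatment visit as the withdrawal visit for leavers, which four places in the documents support. It concerns only patients who leave the study; Protocol 3.14.4.1 encourages those who merely stop study drug to keep attending. Severity is minor: the endpoint is exploratory and descriptive, and no error rate, power or primary safety conclusion depends on it.

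**What to change.** In SAP 6.4.1.2:

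- Count a patient as discontinuing only if the preventive stays stopped through scheduled visit 14.
- Count patients who withdraw from the study early as not meeting the endpoint, in line with SAP 6.4.1.1. This also settles patients lost to follow-up without an end-of-treatment visit, whom the section does not address.
- Report patients who stopped the preventive and then withdrew early in a separate row, so that the proportion of all stoppers can still be read.
- State that the denominator is all baseline preventive users in the FAS.

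The cost is a wording change, one extra table row and a slightly less favourable headline proportion. No new data are needed and patient management does not change.

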6.4.1.3. Six-Item Headache Impact Test

Migraine-related disability for CM patients will be assessed using the HIT-6 (see [Appendix C](#)) completed at the time points specified in [Table 1](#) and [Table 2](#) to measure the impact headaches having on his/her ability to function on the job, at school, at home, and in social situations. Each question is answered on the scale ranging with the following response options: 6 points (never), 8 points (rarely), 10 points (sometimes), 11 points (very often), and 13 points (always). The total score is obtained from summation of the 6 question points. The HIT-6 total score ranges between 36 and 78, with larger scores reflecting greater impact. If one or more items are missing, then the total score is missing.

6.4.1.4. Migraine Disability Assessment Questionnaire

The MIDAS questionnaire ([Appendix D](#)) is a 5-item instrument developed to assess headache-related disability based on lost days of activity in 3 domains (work, household work, and nonwork) over the previous 3 months. The total of the scores of the first 5 questions is used for grading of disability, with scores of 0 to 5, 6 to 10, 11 to 20, and ≥ 21 interpreted as disability grades 1 (little or no disability), 2 (mild disability), 3 (moderate disability), and 4 (severe disability), respectively. It has been shown to be reliable and valid for migraine, with substantially higher scores in migraine cases than non-migraine cases ([Stewart et al 1999a](#), [Stewart et al 1999b](#)).

Patients with EM will complete the MIDAS questionnaire at time points specified in [Table 1](#) and [Table 2](#).

6.4.1.5. Migraine Specific Quality of Life

The 14-item MSQOL ([Appendix E](#)) questionnaire is designed to measure how migraines affect and/or limit daily functioning across 3 domains: Role Function-Restrictive domain comprising 7 items assessing how migraines limit one's daily social and work-related activities; Role Function-Preventive domain comprising 4 items assessing how migraines prevent these activities, Emotional Function domain comprising 3 items assessing the emotions associated with migraines. Raw dimension scores are computed as a sum of item responses and rescaled from a 0 to 100 scale such that higher scores indicate better health-related quality of life. [Appendix F](#) provides the scoring instructions on how to rescale the raw score to the scales that will be used for the analysis.

Patients will complete the MSQOL at time points specified in [Table 1](#) and [Table 2](#).

6.4.1.6. EuroQol-5 Dimension Questionnaire

The EQ-5D-5L questionnaire ([Appendix G](#)) is a standardized questionnaire that assesses overall state of health. The EQ-5D consists of 2 parts. In Part 1, patients rate their health state in 5

domains: mobility, self-care, usual activities, pain/discomfort, and mood, using a scale of 1 to 5 where 1=no problems, 2=slight problems, 3=moderate problems, 4=severe problems, and 5=extreme problems. In Part 2, patients rate their health state on a 100 mm visual analog scale (VAS); a rating of 0 represents the worst imaginable health state, and a rating of 100 represents the best imaginable health state.

Patients will complete the EQ-5D-5L at the time points specified in in [Table 1](#) and [Table 2](#).

6.4.1.7. Patient Global Impression of Change Scale

The PGIC scale ([Appendix H](#)) is a validated generic tool for assessment of overall change in the severity of illness following treatment. Patients will rate how they feel now compared with how they felt before receiving study drug on a 7-point scale where 1=no change (or condition got worse); 2=almost the same, hardly any change at all; 3=a little better, but no noticeable change; 4=somewhat better, but the change has not made any real difference; 5=moderately better, and a slight but noticeable change; 6=better, and a definite improvement that has made a real and worthwhile difference; and 7=a great deal better, and a considerable improvement that has made all the difference.

Based on the PGIC assessment, a dichotomous scale of “ Yes” or “No” will be derived. A favorable change is score of 5-7 = 'Yes', which means there is significant improvement with the treatment. If the response is 1-4 = 'No', it is considered no significant change.

Patients will complete the PGIC scale at time points specified in [Table 1](#) and [Table 2](#).

6.4.1.8. Two-Item Patient Health Questionnaire/9-Item Patient Health Questionnaire

The PHQ ([Appendix I](#)) is a 9-item questionnaire with each item corresponding to 1 criterion of the Diagnostic and Statistical Manual for Mental Disorders 4th edition diagnostic criteria for major depressive disorder. Each of the items is scored on a scale of 0 (“not at all”) to 3 (“nearly every day”) based on the frequency of symptoms ([Spitzer et al 1999](#)). The PHQ-2 was developed from the PHQ-9 to rapidly screen for depression. The PHQ-2 and the PHQ-9 are validated measures for detecting and monitoring depression, anxiety, and somatization ([Kroenke et al 2010](#)).

Patients will complete the PHQ-2 at time points specified in [Table 1](#) and [Table 2](#). If the PHQ-2 is positive (ie, a score ≥ 3), patients will complete questions 3 through 9 [unique questions] of the PHQ-9. If the PHQ-2 is negative (ie, a score < 3), the scores for the questions 3 through 9 are imputed '0'.

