3.6. Exploratory Measures and Time Points

Efficacy will be assessed at time points specified in Table 1 (patients rolling over from the pivotal efficacy studies) and Table 2 (patients not rolling over from the pivotal efficacy studies) using the following exploratory efficacy measures:

- exploratory efficacy endpoints derived from headache data (ie, occurrence of headache, duration of headache, maximum severity of headache, and acute migraine-specific medication use), which will be collected using an electronic headache diary device
- HIT-6 (patients with CM only)
- MIDAS questionnaire (patients with EM only)
- PHQ-2/PHQ-9 (Note: Patients will first respond to the PHQ-2. They will respond to questions 3 through 9 [unique questions] of the PHQ-9 only if the PHQ-2 is positive.)
- MSQOL questionnaire

- EQ-5D-5L questionnaire
- PGIC scale
- WPAI questionnaire

A description of the efficacy measures is provided in Section 6.

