6.5. Two-Item Patient Health Questionnaire/9-Item Patient Health Questionnaire

The PHQ is a 9-item questionnaire with each item corresponding to 1 criterion of the Diagnostic and Statistical Manual for Mental Disorders 4th edition diagnostic criteria for major depressive disorder. Each of the items is scored on a scale of 0 (“not at all”), 1 (“several days”), 2 (“more than half the days”), and 3 (“nearly every day”) based on the frequency of symptoms during the past 2 weeks (Spitzer et al 1999). The PHQ-2 was developed from the PHQ-9 to rapidly screen for depression and consists of the first 2 questions from the PHQ-9. The PHQ-2 and the PHQ-9 are well-validated measures for detecting and monitoring depression, anxiety, and somatization (Kroenke et al 2010).

Patients will complete the PHQ-2 at time points specified in Table 1 (patients rolling over from the pivotal efficacy studies) and Table 2 (patients not rolling over from the pivotal efficacy studies). If the PHQ-2 is positive (ie, a score ≥ 3), patients will complete questions 3 through 9 [unique questions] of the PHQ-9.

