9.5.4.4. Exploratory Efficacy Analysis

All efficacy variables will be summarized descriptively. For continuous variables, descriptive statistics (n, mean, SD, standard error of mean, median, minimum, and maximum) will be provided for actual values and changes from baseline to each visit. For categorical variables, frequency and percentage will be provided. For rollover patients, their baseline is defined as the baseline in the pivotal efficacy studies.

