- proportion of patients discontinuing concomitant preventive medications during the treatment period
- mean change from baseline (day 0) in disability score in patients with CM, as measured by the HIT-6, at visits 8 and 14
- mean change from baseline (day 0) in disability score in patients with EM, as measured by the MIDAS questionnaire, at visits 8 and 14
- mean change from baseline (day 0) in quality of life, as measured by the MSQOL questionnaire, at visits 8 and 14
- mean change from baseline (day 0) in patient health status, as measured by the EQ-5D-5L questionnaire, at visits 8 and 14
- assessment of patient satisfaction, as measured by the PGIC scale at visits 3, 5, 8, 11, and 14
- mean change from baseline (day 0) in patient depression status, as measured by the PHQ-2 and PHQ-9, at visits 8 and 14
- mean change from baseline (day 0) in patient work productivity and activity impairment, as measured by the WPAI questionnaire, at visits 8 and 14

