4.2. Specification of Baseline Values

For the patients rolling over from the pivotal efficacy studies, their baseline values will be the baseline values from the pivotal studies.

Eligible new patients will enter a 28-day run-in period during which they will complete daily electronic headache diary entries. The efficacy baseline values are based on the run-in period data. If the run-in period is greater than 28 days, the baseline values will be normalized to 28-day.

The efficacy variable baseline values during the 28-day run-in period that will be derived from the e-diary include

- total number of migraine days
- total headache days of at least moderate severity
- total headache days of any severity
- total number of days of use of any acute headache medication
- total number of headache hours of at least moderate severity
- total number of headache hours of any severity
- total number of days with nausea or vomiting
- total number of days with photophobia and phonophobia

Other efficacy baseline values that will be measured on day 0 include

- disability score in patients with CM, as measured by the HIT-6 ([Appendix C](#))
- disability score in patients with EM, as measured by the MIDAS questionnaire ([Appendix D](#))
- quality of life, as measured by the MSQOL questionnaire ([Appendix E](#))
- health status, as measured by the EQ-5D-5L questionnaire ([Appendix G](#))
- patient depression status, as measured by the PHQ-2 and the PHQ-9 ([Appendix I](#))

- patient work productivity and activity impairment, as measured by the WPAI questionnaire ([Appendix J](#))

For safety data, new patient's baseline values will be the last values prior to the 1st dose of study drug.

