5.3. Demographics and Baseline Characteristics

The demographics and baseline characteristics including age, sex, race, ethnicity, country, region, weight, height, body mass index, years of migraine, concomitant preventive medication use for migraine, use of topiramite or onabotulinumtoxinA for migraine in the past, and any triptans/ergots during baseline will be summarized for the ITT population, FAS, safety population and ADA analysis set.

The baseline e-diary efficacy variables listed in Section 4.2, and the baseline scores for the assessments of migraine impairment and quality of life including HIT-6 for CM patients, MIDAS for EM patients, MSQOL, EQ-5D-5L measurements, PHQ-9, and WPAI will be summarized.

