6.4.2.8. Patient Health Questionnaire

The change from baseline in total PHQ-9 score and 95% confidence interval will be summarized by visits/months.

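### WPAI activity impairment is summarised only in employed patients, and the only PHQ change named is a PHQ-9 total in which unasked items count as 0

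*SAP*

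**What the plan says.** **WPAI.** Protocol 6.9 and SAP 6.4.1.9 describe two impact questions, one on productivity at work and one on everyday activity away from it. SAP 6.4.1.9 derives four scores: three work scores (from Q2, Q4 and Q5) and percent activity impairment (Q6/10). SAP 6.4.2.9 opens with a restriction to patients in current employment and lists all four scores under it.

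**PHQ collection.** Protocol 3.6 sets the gate: "They will respond to questions 3 through 9 [unique questions] of the PHQ-9 only if the PHQ-2 is positive". Protocol 6.5 gives the cut-off: with a PHQ-2 score of 3 or more, "patients will complete questions 3 through 9 [unique questions] of the PHQ-9".

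**PHQ scoring and analysis.** SAP 6.4.1.8 adds that, with PHQ-2 below 3, "the scores for the questions 3 through 9 are imputed" as zero. The analysis paragraph, SAP 6.4.2.8, is one sentence: "The change from baseline in total PHQ-9 score and 95% confidence interval will be summarized by visits/months".

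**Endpoints and baseline.** The endpoint in SAP 2.2.3 is the mean change from day 0 "in patient depression status, as measured by the PHQ-2 and PHQ-9, at visits 8 and 14". SAP 4.2 lists a day 0 value for "patient depression status, as measured by the PHQ-2 and the PHQ-9". The baseline table list in SAP 5.3 names PHQ-9 but not PHQ-2: "MSQOL, EQ-5D-5L measurements, PHQ-9, and WPAI will be summarized". For rollover patients, SAP 4.2 takes baseline from the pivotal studies.

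**The concern.** The WPAI restriction suits the three work scores, which need working hours or a job to refer to. It does not suit Q6. As written, patients without a job drop out of a score that needs no employment, and no other SAP paragraph summarises it for them. The reported activity result then describes the employed subset only.

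The PHQ total combines two kinds of number: answers, and zeros standing in for questions that were not put. A patient who moves across the PHQ-2 cut-off gains or loses the whole of items 3 to 9 at once, whether or not those symptoms changed. A reader of a table labelled as PHQ-9 change would take it as observed movement on nine items. PHQ-2 has no such problem, since every respondent answers it, yet it is not named in SAP 6.4.2.8. The SAP treats another questionnaire differently: under SAP 6.4.1.3 the HIT-6 total is missing if any item is missing.

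**Working it through.** The plan gives no figure to reproduce here. The check sets passages side by side and works through the scoring rule.

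**WPAI.** Each score against what it needs:
- Work time missed, Q2/(Q2+Q4): hours missed and hours worked, so employment.
- Impairment while working, Q5/10: employment.
- Overall work impairment, built from the two above: employment.
- Activity impairment, Q6/10: everyday activity, so no employment.

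The restriction therefore fits 3 of the 4 scores. The documents do not give the number of patients without employment.

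**PHQ inputs** (SAP 6.4.1.8; Protocol 6.5): nine items scored 0 to 3; PHQ-2 is the first two; cut-off 3.
- P = PHQ-2, range 0 to 6.
- S = sum of items 3 to 9, range 0 to 7 × 3 = 21.
- SAP total: G = P + S if P ≥ 3, and G = P if P < 3.
- All-items total: P + S.

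**Ranges.** With P < 3, G can only be 0 to 2, while P + S could be 0 to 2 + 21 = 23. With P ≥ 3, G is 3 to 6 + 21 = 27.

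**Change with the rule applied at both visits.**
- P from 3 to 2, S unchanged: G changes by 2 − (3 + S) = −(1+S); the all-items change is −1. S = 3 gives −4, S = 7 gives −8, S = 14 gives −15. The arithmetic bound, S = 21, gives −22.
- P from 2 to 3, S = 7 unchanged: G changes by (3 + 7) − 2 = +8; the all-items change is +1.
- P below 3 at both visits: G can change only between −2 and +2, whatever happens on items 3 to 9.

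**Group mean.** If a net fraction f of patients crosses downward with S unchanged, the mean change shifts by −f × S. The documents give neither f nor S. With assumed values:
- f = 5%, S = 3: −0.15
- f = 10%, S = 7: −0.70
- f = 20%, S = 14: −2.80

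A net upward crossing reverses the sign.

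**To whom this applies.** New patients have PHQ at day 0 and visits 8 and 14 under this protocol's gate (Protocol Table 2), so the arithmetic holds for them. Rollover patients have PHQ only at visits 8 and 14 here (Protocol Table 1). By plan they are 867 + 675 = 1542 of 1842, or 84% (SAP 2.3). The documents do not say how items 3 to 9 were asked or scored at the pivotal baseline. Take a rollover patient with P = 2 and S = 7 throughout. If the baseline was gated and zero-scored in the same way, G goes from 2 to 2, a change of 0. If all nine items had been asked and counted at baseline, it goes from 9 to 2, a change of −7 with nothing altered. Both are assumptions.

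**The case against.** Much can be said for the plan as it stands.

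- **The zero rule is open.** The gate is in the protocol and the scoring is stated in the SAP. A reader might infer an undisclosed imputation; there is none. What stands is that the label in SAP 6.4.2.8 does not carry the rule into the table.
- **PHQ-2 and WPAI change have not been dropped.** A reader might infer this from SAP 6.4.2.8 and 6.4.2.9, which do not name them. But SAP 2.2.3 lists both changes as endpoints, SAP 6.4 refers to that list, and Protocol 9.5.4.4 states "All efficacy variables will be summarized descriptively" and includes changes from baseline. Naming them is a clarification. That general wording does not undo the explicit employment restriction on Q6.
- **The unseen change below the cut-off comes from data collection.** Items 3 to 9 are not asked there under the protocol, so no SAP change can recover them. This stands in full.
- **A biased PHQ-9 result is not shown.** A reader might infer that the mean overstates improvement. The crossing share and S are unknown, crossings can go either way, and the baseline rule is not shown for 84% of planned patients. This also stands.
- **The stakes are low.** SAP 4.4 and 6.4.2 exclude inference and testing, and suicidality is assessed separately by the eC-SSRS.

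**Conclusion.** The point holds as a minor one, in two parts. First, the employment restriction is misplaced for 1 of the 4 WPAI scores; this follows from the SAP's own description of Q6. Second, the only PHQ change named in SAP 6.4.2.8 is a gated total. Where the gate applies at both visits, crossing from PHQ-2 of 3 to 2 with S unchanged shows −(1+S) for a one-point change.

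The second part is confirmed for new patients, about 300 of 1842 planned, and unconfirmed for rollover patients. Neither the size nor the direction of an effect on any group mean can be stated. Both parts rest on the SAP body text, since the questionnaires in SAP Appendices I and J are not shown in the copy reviewed. Because the endpoints are exploratory and descriptive, what is affected is how the tables are read; no error rate or primary safety conclusion is touched.

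**What to change.** - **SAP 6.4.2.9:** summarise percent activity impairment (Q6) in all respondents and keep the employment restriction for the three work scores. For clarity, name the change from baseline that the endpoint already calls for.
- **SAP 6.4.2.8:** add change from baseline in PHQ-2 (0 to 6) with a 95% CI, and the number (%) with PHQ-2 of 3 or more at baseline and visits 8 and 14, in the style of the MIDAS grade table in SAP 6.4.2.4. Add PHQ-2 to the baseline list in SAP 5.3.
- **PHQ-9 table:** keep the total, with a footnote that items 3 to 9 are not asked when PHQ-2 is below 3 and are then set to 0. State how the pivotal-study baseline was collected and scored for rollover patients.

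The cost is a few sentences of SAP text, one footnote and a few tables from data already collected. Patient procedures do not change.
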